### 11.2 Study Populations

#### 11.2.1 Analysis Population for the Safety Analyses

The intent-to-treat (ITT) population will include all subjects assigned to study medication who receive at least 1 dose of study medication. All safety analyses will be performed using the ITT population.

#### 11.2.2 Analysis Populations for the Efficacy Analyses

The modified intent-to-treat (MITT) population for Hb or RBC count will include subjects who receive at least 1 dose of study medication, have a pre-treatment average defined as the average of the qualifying screening value and the baseline value, and at least one post-baseline measurement. The MITT population for other parameters will include subjects who receive at least 1 dose of study medication, have at least one pre-treatment value, and at least one post-baseline measurement.

The per protocol (PP) population will consist of the subjects in the MITT population who have completed the study and have efficacy data through Week 6, have a study medication compliance of  $\geq 80\%$ , and do not have any major protocol deviations.

As sensitivity analyses, efficacy endpoints will also be analyzed using the PP population.

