### 5.1 Primary Objective and Endpoint

The primary objective of this study is to assess the dose-response relationship between oral vadadustat once daily dosing for 6 weeks and the change in Hb in Japanese subjects with anemia secondary to NDD-CKD; in order to define the starting dose for use in Phase 3 clinical studies in Japan.

The primary endpoint that will be used to assess this objective is the mean change in Hb levels from pre-treatment to the end of the primary efficacy period (Week 6).

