Individual subject's study data (from screening to Week 6) will be cleaned and locked during the 4-week, blinded, dose adjustment period.

At the Week 10 visit, treatment assignment will be unblinded on an individual subject basis. Subjects who were randomized to receive placebo will end study participation after unblinding at the Week 10 visit. Subjects who were randomized to receive 1 of the 3 vadadustat doses will continue receiving vadadustat during the 6-week, open-label extension period.

Vadadustat treatment will stop after the extension period has been completed (Week 16) and subjects will continue in a 2-week follow-up safety period (Week 17-18).

The clinical and safety assessments will be performed as described in [Section 9.3](#) and as listed in [Appendix A](#).

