#### 8.2.8 Rescue Therapy Guidelines

The following rescue therapy guidelines are provided to ensure the safety of study subjects and to standardize the use of rescue in the study.

- **ESA rescue:** ESA rescue therapy may be considered based on the investigator's judgment if a subject:
  - Experiences a clinically significant worsening of anemia or symptoms of anemia, and
  - Exhibits Hb level <9.0 g/dL
- **RBC transfusion:** Investigators should use their local institution's transfusion guidelines when determining whether to transfuse a study subject.

Subjects who initiate rescue therapy will be required to stop study drug treatment and will be discontinued from the study.

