## 7.6 Subject Completion and Individual Subject Discontinuation

### 7.6.1 Subject Completion

A subject randomized to receive placebo will be considered as having completed the study after completing participation in the Week 10 (unblinding) visit.

A subject randomized to receive vadadustat will be considered as having completed the study after completing participation in the Week 18 visit (end of the 2-week safety follow-up period).

Note that for subjects who discontinue study drug due to an excess Hb response during the primary efficacy period, Hb levels will be monitored weekly via lab evaluation until the subject no longer exhibits an excess Hb response.

See [Section 10.3.6](#) for information regarding follow-up of unresolved events.

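### The per-protocol set for the Week 6 endpoint requires study completion, which means Week 10 on placebo but Week 18 on vadadustat

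*Protocol*

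**What the plan says.** Section 11.2.2 defines the PP set as "the subjects in the MITT population who have completed the study and have efficacy data through Week 6", with study drug compliance of at least 80% and no major protocol deviation. It gives no time window for compliance or deviations. The set's use is stated directly: "As sensitivity analyses, efficacy endpoints will also be analyzed using the PP population". The primary endpoint (Section 5.1) is the change in Hb from pre-treatment to Week 6.

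Section 7.6.1 defines study completion separately by arm:

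- Placebo: "A subject randomized to receive placebo will be considered as having completed the study after completing participation in the Week 10 (unblinding) visit".
- Vadadustat: "A subject randomized to receive vadadustat will be considered as having completed the study after completing participation in the Week 18 visit".

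On timing, Section 6.1 says "Individual subject's study data (from screening to Week 6) will be cleaned and locked during the 4-week, blinded, dose adjustment period" and "At the Week 10 visit, treatment assignment will be unblinded on an individual subject basis". Section 8.2.8 adds a route out of the study: "Subjects who initiate rescue therapy will be required to stop study drug treatment and will be discontinued from the study".

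The file holds three successive versions of the protocol. The PP sentence is identical in the first two, and Section 7.6.1 is the same in all three. The third breaks off in Section 8.1.4, so its Section 11.2.2 cannot be read.

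**The concern.** A sensitivity analysis of a Week 6 outcome should not depend on what happens after Week 6, and least of all on follow-up that differs in length by arm. Under this definition, a vadadustat subject with complete, compliant data to Week 6 who leaves at Week 12 drops out of the PP set. A placebo subject cannot be dropped for leaving at that time, because placebo participation has already ended.

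The later exits need not be random. Rescue with an erythropoiesis-stimulating agent or transfusion ends participation, and a poor Hb responder at Week 6 is a plausible later rescue case. If exits follow Hb response, the PP slope can agree or disagree with the MITT slope because of selection alone. The protocol also builds a blinded cleaning and lock step around each subject's data to Week 6, but PP status for a vadadustat subject stays open until Week 18, after the code has been broken.

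**Working it through.** **Inputs.** Section 11.1: 12 subjects per group; expected Hb changes 0, 0.5, 0.7 and 1.2 g/dL at 0, 150, 300 and 600 mg; SD 0.68; linear regression on dose; stated power above 85%. Section 11.5: two-sided 0.05. Section 7.6.1: completion at Week 10 or Week 18. Section 6.1: unblinding at Week 10. No dropout rate is given, so every loss rate below is an assumption.

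**1. The plan's own figure.** Mean dose = (0 + 150 + 300 + 600)/4 = 262.5 mg. Sum of squared dose deviations over the four doses = 196,875. Sum of cross-products with the expected changes = -112.5 × 0.5 + 37.5 × 0.7 + 337.5 × 1.2 = 375. Slope = 375/196,875 per mg, or 1.14 g/dL per 600 mg. A simulation of 10,000 trials gives 98.6% power, so the stated lower bound holds. The sample size is not at issue.

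**2. Required stay after the endpoint.** Placebo: 10 - 6 = 4 weeks. Vadadustat: 18 - 6 = 12 weeks. The difference is 8 weeks, all of it after unblinding (18 - 10 = 8). Weeks 7-10 are blinded and count for every arm.

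**3. Subjects dropped despite Week 6 data.** Assume 10-20% of vadadustat subjects are lost over Weeks 6-18.

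- Vadadustat: 36 × 0.10 = 3.6 to 36 × 0.20 = 7.2.
- Placebo at the same weekly rate: 12 × [1 - 0.90^(4/12)] = 0.4 to 12 × [1 - 0.80^(4/12)] = 0.9.

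Alternatively, let loss be *a* in Weeks 6-10 (all arms) and *c* in Weeks 10-18 (vadadustat only). Placebo kept = 12(1 - a); vadadustat kept = 36(1 - a)(1 - c). With a = c = 5%, 11.4 of 12 and 32.5 of 36 are kept. With a = 10% and c = 20%, 10.8 of 12 and 25.9 of 36 are kept.

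**4. Effect on the PP slope.** Extra loss was applied to the vadadustat arms only, with 10,000 trials per row. In the Hb-related rows, the log-odds of loss are log[q/(1 - q)] ± 2(y - m)/0.68, where y is the Week 6 Hb change, m is the mean expected change over the active arms (0.8, or 0 with no dose effect) and q = 5, 10 or 20%. This is a strong dependence, chosen for illustration. With all 48 subjects, the slope is 1.14-1.15 and is significant in 98.7-98.9% of trials.

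| Later loss | Vadadustat kept | Slope per 600 mg | Significant |
|---|---|---|---|
| Random, 5 / 10 / 20% | 95 / 90 / 80% | 1.15 / 1.15 / 1.17 | 98.6 / 98.3 / 97.5% |
| Low responders leave | 85 / 79 / 69% | 1.18 / 1.22 / 1.28 | 99.2 / 99.3 / 99.7% |
| High responders leave | 85 / 78 / 69% | 0.95 / 0.89 / 0.80 | 92.6 / 87.0 / 76.3% |
| No dose effect, random | 95 / 90 / 80% | within 0.005 of 0 | 5.2 / 5.1 / 5.3% |
| No dose effect, low leave | 87 / 80 / 70% | 0.11 / 0.16 / 0.24 | 6.8 / 9.3 / 12.8% |
| No dose effect, high leave | 87 / 80 / 70% | -0.11 / -0.16 / -0.24 | 7.1 / 8.7 / 13.6% |

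**The case against.** **Week 6 may have been meant to limit both conditions.** The sentence can be read that way, and Section 7.6.1 does not mention analysis sets. But the grammar gives two conditions, and the protocol is explicit when it means the shorter period: Section 6.1 speaks of completing the primary efficacy period and Appendix A of completing Week 6. Section 11.4, in the same chapter, uses study completion for overall disposition. Between the first two protocol versions the MITT paragraph was rewritten and the PP sentence left alone. Even on the lenient reading, a programmer applying Section 7.6.1 would build the wrong set.

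**The governing text is not fully visible.** This stands. The last version's Section 11.2.2 may differ.

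**No bias is demonstrated.** This also stands. Random loss does almost nothing, and the distortions come from an assumed model. The high-responder case is the less plausible one, because the mandatory stop for excess Hb applies to the primary efficacy period (Sections 7.6.2 and 8.2.4), whereas Section 8.2.7 handles high values after Week 6 by dose reduction or interruption. Rescue remains an exit for low responders.

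A reader might go further and infer that the primary result is compromised, that all of the selection happens unblinded, or that the PP analysis is the only check on the primary result. The documents do not support any of these. The MITT analysis does not use completion status. Weeks 7-10 are blinded and apply to all arms. The PP analysis is the only sensitivity analysis Section 11.2.2 names, but Section 11.5 leaves the full set of efficacy outcomes to the SAP, which is not at hand and may add others.

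**Conclusion.** The definition is wrong as written and should be corrected. In the latest version whose Section 11.2.2 can be read, PP membership for a Week 6 endpoint depends on remaining 8 weeks longer in the vadadustat arms than on placebo, and for vadadustat it cannot be settled at the Week 6 lock. That much follows from the protocol's own definitions.

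The consequence is confined to the PP sensitivity analysis, and its size cannot be derived from the documents. It is negligible if later loss is unrelated to Hb. Under the strong Hb-related loss assumed above (13-31% of vadadustat subjects), the planned PP slope of about 1.14 moves to between 0.80 and 1.28 g/dL per 600 mg, and with no dose effect the type I error is about 7-14% instead of 5%. These figures illustrate what could happen and are not a forecast.

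**What to change.** - For Week 6 endpoints, replace the study-completion condition with completion of the primary efficacy period, meaning that a Week 6 Hb is available. Assess compliance and major deviations from Day 1 to Week 6 only.
- Fix each subject's membership at the Week 6 lock, before that subject's code is broken.
- Do not add a condition of still being on study drug. It would remove subjects who reduced or stopped drug because the protocol's excess-Hb rule required it, which is again selection on the outcome. Section 7.6.3 brings the end-of-treatment assessments forward for those who stop early, so some may lack a Week 6 value; report their number by arm.
- Define a separate PP set for the Week 16 endpoints, where a later completion condition is natural.
- Check whether Section 11.2.2 of the final protocol version, and the SAP, carry the same wording.

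The cost is a few sentences in the protocol and SAP. Visits, data collection and treatment do not change.

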### 11.3 Analysis of Demographics and Pretreatment Variables

Descriptive statistics (eg, number of subjects, mean, standard deviation (SD), median, minimum, and maximum) will be generated for selected continuous variables (including age, selected laboratory assays, and vital signs). The number and percentage of subjects in each class of categorical demographic and baseline variables (eg, gender, ethnicity, race, and CKD stage) will be tabulated. Individual subject demographic and baseline characteristic data will be listed.

### 11.4 Disposition of Subjects

The number of subjects who are randomized, discontinued, or complete the study and reasons for discontinuation will be summarized in tabular format.

### 11.5 Efficacy and PD Analyses

The entire set of efficacy outcomes will be defined in the statistical analysis plan (SAP). In addition to the primary endpoint analysis defined above, the following efficacy endpoints will also be assessed:

- Actual values and change (absolute and percent) from baseline in Hb, HCT, RBC count, and reticulocyte count (both absolute and percent)
- Actual values and change (absolute and percent) from baseline in iron, TIBC, TSAT, ferritin (both absolute and percent), and hepcidin

For purposes of analysis, a pre-treatment average (defined as the average of 2 samples obtained prior to treatment [ie, the qualifying screening value and baseline value]) will be used as the baseline value for Hb and RBC count, and last observation before the first dose of study medication will be used as baseline for other parameters.

Changes from baseline of efficacy and PD parameters will be summarized using descriptive statistics by treatment groups and each scheduled assessment, and results will be displayed using box plots.

Linear regression analysis will be performed for Hb change from baseline to Week 6, to assess the vadadustat dose-response relationship. Similar analysis will be performed for change from baseline to Week 6 of reticulocyte count (both absolute and percent), hematocrit, and RBC count.

Also, similar linear regression analysis will be performed for change from baseline to Week 6 of the iron indices (ie, iron, TIBC, ferritin, and TSAT) and hepcidin will be evaluated.

All tests of significance will be performed using a 0.05 two-sided significance level.

## **11.6 Safety Analyses**

The reporting of safety data is descriptive, and will include all subjects who receive at least one dose of study medication. The following variables are the safety endpoints: adverse events, vital signs, ECGs, components of the CBC, and VEGF.

AEs will be summarized based on the frequency of AEs and their severity for all treated subjects. Overall safety and tolerability will be assessed with treatment-emergent AEs, laboratory results, and other safety variables including summaries of vital signs and ECGs. As appropriate, summaries may also include change from baseline and shift tables. All AEs will be coded using the Medical Dictionary for Regulatory Activities (MedDRA) and summarized by dose level. Data will be summarized using preferred term and primary system organ class.

## **11.7 PK Analyses**

At the Week 4 visit, pre-dose plasma concentrations of vadadustat and its metabolites will be obtained to evaluate for accumulation of study medication.

# **12 DATA HANDLING AND RECORD KEEPING**

## **12.1 Case Report Forms (CRFs)**

This study will utilize an EDC system to manage data collection during this trial. The system is fully Code of Federal Regulations 21 part 11 compliant. An EDC system contains certain functionality including, but not limited to, a graphical user interface to help facilitate data entry, a data validation element to check user data, and a reporting function to assist with the review and analysis of data. CRFs available through this system are required and should be completed for each randomized subject.

Any form of data from the electronic system are the sole property of the sponsor and should not be made available in any form to third parties, except for authorized representatives of the sponsor or appropriate regulatory authorities, without written permission from the sponsor.

The investigator has ultimate responsibility for the accuracy, authenticity, and timely collection and reporting of all clinical, safety, and laboratory data entered in the EDC or any other data collection forms. The CRFs must be signed electronically by the Investigator to attest that the data contained on the CRFs is true.

In most cases, the source documents are contained in the subject's chart at the hospital or the physician's office. In these cases, data collected on the CRFs must match the data in those charts.

## **12.2 Record Retention**

To enable evaluations and/or audits from regulatory authorities or the sponsor, the investigator agrees to keep records, including the identity of all participating subjects (sufficient information to link records, eg, CRFs and hospital records), all original signed Informed Consent Forms, copies of all CRFs, SAE forms, source documents, detailed records of drug disposition, and

adequate documentation of relevant correspondence (eg, letters, meeting minutes, telephone calls reports). The records should be retained by the investigator according to the International Conference on Harmonisation (ICH), local regulations, or as specified in the Clinical Study Agreement, whichever is longer.

If the investigator becomes unable for any reason to continue to retain study records for the required period (eg, retirement, relocation), the sponsor should be prospectively notified. The study records must be transferred to a designee acceptable to the sponsor, such as another investigator, another institution, or to the sponsor. The investigator must obtain sponsor's written permission before disposing of any records, even if retention requirements have been met.

## **13 QUALITY CONTROL (QC) AND QUALITY ASSURANCE (QA)**

### **13.1 Study Site Monitoring Visits**

During study conduct, the sponsor or its designee will conduct periodic monitoring visits to ensure that the protocol and Good Clinical Practice (GCP) are being followed. The monitors will review source documents to confirm that the data recorded on CRFs is accurate. The investigator/institution will allow the sponsor's monitors or designees and appropriate regulatory authorities direct access to source documents to perform this verification.

The study site may also be subject to quality assurance audits performed by the sponsor or its designees, and/or review by the IRB/IEC, and/or to inspection by appropriate regulatory authorities.

It is important that the investigator(s) and their relevant personnel are available during the monitoring visits and possible audits or inspections and that sufficient time is devoted to the process.

### **13.2 Protocol Deviations**

The investigator should not deviate from the protocol, except where necessary to eliminate an immediate hazard to study subjects. Should other unexpected circumstances arise that will require deviation from protocol-specified procedures, the investigator should consult with the sponsor or designee (and IRB or IEC, as required) to determine the appropriate course of action.

The site should document all protocol deviations in the subject's source documents. In the event of a major protocol deviation, the site should notify the sponsor or its designee (and IRB or IEC, as required). Major protocol deviations include, but are not limited to, those that involve fraud or misconduct, increase the health risk to the subject, or confound interpretation of primary study assessments.

## **14 STUDY DISCONTINUATION/INVESTIGATIVE STUDY SITE TERMINATION**

The sponsor reserves the right to discontinue the trial prior to inclusion of the intended number of subjects, but intends only to exercise this right for valid scientific or administrative reasons. After such a decision, the investigator must contact all participating subjects within a time period specified by the sponsor to inform them of the decision to discontinue the trial.

## **14.1 Criteria for Premature Termination or Suspension of the Study**

The following criteria may result in either temporary suspension or early termination of the study:

- New information regarding the safety or efficacy of the study medication that indicates a change in the known risk/benefit profile for the compound, such that the risk/benefit is no longer acceptable for subjects participating in the study.
- Major violation of GCP that compromises the ability to achieve the primary study objectives or compromises subject safety.

The sponsor reserves the right to discontinue the trial for other valid administrative reasons.

## **14.2 Criteria for Premature Termination or Suspension of Investigational Sites**

A study site may be terminated prematurely or suspended if the site (including the investigator) is found to be in major violation of GCP, protocol, contractual agreement, or is unable to ensure adequate performance of the study.

## **14.3 Procedures for Premature Termination or Suspension of the Study or Investigational Site(s)**

In the event that the sponsor elects to terminate or suspend the study or the participation of an investigational site, a study-specific procedure for early termination or suspension will be provided by the sponsor; the procedure will be followed by applicable investigational sites during the course of termination or study suspension.

# **15 ETHICS**

## **15.1 Ethical Conduct of the Study**

The study will be conducted in accordance with the Declaration of Helsinki on Ethical Principles for Medical Research Involving Human Subjects, adopted by the General Assembly of the World Medical Association (2013).

In addition, the study will be conducted in accordance with the protocol, the ICH guideline on GCP, and applicable local regulatory requirements and laws.

## **15.2 Institutional Review Board (IRB) / Independent Ethics Committee (IEC)**

It is the responsibility of the investigator to have prospective approval of the study protocol, protocol amendments, informed consent forms, and other relevant documents, (eg, recruitment advertisements, if applicable) from the IRB/IEC. All correspondence with the IRB/IEC should be retained in the Investigator File. Copies of IRB/IEC approvals should be forwarded to the sponsor.

The only circumstance in which an amendment may be initiated prior to IRB/IEC approval is where the change is necessary to eliminate apparent immediate hazards to the subjects. In that event, the investigator must notify the IRB/IEC and the sponsor in writing immediately after the implementation.

### **15.3 Subject Information and Consent**

Prior to inclusion in the study, it is the responsibility of the investigator to give each subject (or the subject's acceptable representative) full and adequate verbal and written information regarding the objective and procedures of the trial and the possible risks involved. The subjects must be informed about their right to withdraw from the trial at any time.

Furthermore, it is the responsibility of the investigator, or a person designated by the investigator, to obtain signed informed consent from each subject or the subject's legally acceptable representative prior to inclusion in the trial. The investigator will retain the original of each subject's signed consent form.

The informed consent form must be in compliance with ICH GCP, local regulatory requirements, and legal requirements. The informed consent form used in this study, and any changes made during the course of the study, must be prospectively approved by both the IRB/IEC and sponsor before use.

